### **11.6.1. Interim Safety Analysis**

An independent Data Monitoring Committee (DMC) will perform an unblinded safety review while subjects in the study receive GC4419/Placebo (Section 14.4).

## **11.7. Primary Efficacy Analysis**

### **11.7.1. Primary Analysis**

The primary endpoint of 28-day mortality will be compared between the GC4419 and control group using an exact Cochran-Mantel-Haenszel (CMH) test stratified by age group (<60 vs  $\geq$ 60 years) at the two-sided 0.05 Type I error rate. The measure of association will be the CMH stratified relative risk of death by Day 28 along with an asymptotic 95% exact confidence interval. For each age stratum, 28-day mortality will be presented descriptively. Should any chance imbalance occur between the groups for important baseline prognostic factors, the effect of these covariates on the inference on treatment may also be examined through logistic regression or similar methods.

### **11.7.2. Secondary and Exploratory Analyses**

Secondary and exploratory endpoints will be analyzed descriptively, and results tabulated. As appropriate, percentages and 95% confidence intervals will be calculated.

## **12. DIRECT ACCESS TO SOURCE DATA/DOCUMENTS**

### **12.1. Study Monitoring**

In accordance with International Conference on Harmonisation Good Clinical Practice (ICH GCP) guidelines, the study monitor must have direct access to the investigator's source documentation in order to verify the consistency of the data recorded in the electronic CRFs.

The monitor is responsible for routine review of the electronic CRFs at regular intervals throughout the study, to verify adherence to the protocol, and the completeness, consistency and accuracy of the data being entered on them. The monitor should have full access to any patient records needed to verify the entries on the electronic CRFs. The investigator agrees to cooperate with the monitor to assure that any follow-up items identified in the course of these monitoring visits are resolved.

The investigator agrees to allow the monitor direct access to all relevant documents and to allocate his/her time and the time of his/her staff to the monitor to discuss findings and any relevant issues.

Due to the timing of this study, it will be necessary to allow monitor remote access to the electronic medical record in order to perform CRF review against source documents remotely.

During site visits, the monitor will:

- Check the progress of the study;
- Review study data collected;
- Conduct source document verification;
- Identify any issues and address their resolution;
- This will be done in order to verify that the:
  - Data are authentic, consistent, accurate, and complete;
  - Safety and rights of subjects are being protected;
  - Study is conducted in accordance with the currently approved protocol (and any amendments), GCP, and all applicable regulatory requirements.

### **12.2. Audits and Inspections**

Authorized representatives of Galera Therapeutics, Inc., a regulatory authority, an IEC or an IRB may visit the site to perform audits or inspections, including source data verification. The purpose of a Galera Therapeutics, Inc. audit or inspection is to systematically and independently examine all study-related activities and documents to determine whether these activities were conducted, and data were recorded, analyzed, and accurately reported according to the protocol, GCP guidelines of the ICH, and any applicable regulatory requirements. The investigator should contact Galera Therapeutics, Inc. immediately if contacted by a regulatory agency about an inspection.

### **12.3. Protocol Compliance**

The investigator is responsible for ensuring the study is conducted in accordance with the procedures and evaluations described in this protocol.

In general, major protocol deviations include deviations from inclusion/exclusion criteria, from concomitant medication restrictions, and from any other protocol requirement that could, at least hypothetically, result in significant risk to the subject and/or affect the outcome of the clinical trial. Major protocol deviations will be noted in the final Clinical Summary Report.

A minor deviation is defined as non-adherence to the protocol procedures or schedule as defined by the protocol or the primary endpoint that does not place the subject at any added or significant risk or affect the data quality or the outcome of the clinical trial (eg, a missed procedure, an out-of-window site visit).

Only subjects who meet protocol-defined eligibility criteria may be enrolled in this clinical trial. If any protocol eligibility criteria or procedures are unclear, the investigator or investigational site personnel should contact the Clinical Research Associate. If the question requires medical interpretation, the sponsor's medical monitor should be consulted. All protocol deviations should be reported to the IRB/IEC according to the standard practices of the investigational site and applicable regulatory requirements.

### **12.4. Protocol Modifications**

Protocol modifications, except those intended to reduce immediate risk to study subjects, may be made only by Galera Therapeutics, Inc. or its representatives. All protocol modifications must be submitted to the IRB/IEC/REB and regulatory authorities in accordance with local requirements. Approval must be obtained before changes can be implemented.

### **12.5. Information Disclosure**

#### **12.5.1. Ownership**

All information provided by Galera Therapeutics, Inc. or its representatives, and all data and information generated by the site as part of the study (other than a subject's medical records), are the sole property of Galera Therapeutics, Inc.

#### **12.5.2. Confidentiality**

All information provided by Galera Therapeutics, Inc. or its representatives, and all data and information generated by the site as part of the study (other than a subject's medical records) will be kept confidential by the investigator and other site staff. Information related to this study is subject to the confidentiality provisions of the Clinical Research Agreement between the investigative site and Galera Therapeutics, Inc.

### **12.5.3. Publication**

All publication or presentation rights for the findings of the clinical investigation under this protocol shall be governed by the appropriate terms of the Clinical Research Agreement between the investigational site and Galera Therapeutics, Inc.

### **13. QUALITY CONTROL AND QUALITY ASSURANCE**

The study will be monitored and managed in accordance with ICH GCP E6.

To ensure compliance with GCPs and all applicable regulatory requirements, Galera Therapeutics, Inc. or its representatives may conduct a quality assurance audit. Regulatory agencies may also conduct a regulatory inspection of this study. Such audits/inspections can occur at any time during or after completion of the study. If an audit or inspection occurs, the investigator and institution agree to allow the auditor/inspector direct access to all relevant documents and to allocate his/her time and the time of his/her staff to the auditor/inspector to discuss findings and any relevant issues.

## **14. ETHICS**

### **14.1. Ethical Conduct of the Study**

The investigator will ensure that this study is conducted in full compliance with the principles of the “Declaration of Helsinki” (version October 2008), ICH guidelines, in particular ICH GCP E6, or with the laws and regulations of the country in which the research is conducted, whichever affords the greatest protection to the study patient. The investigator will also assure that the basic principles outlined in “ICH Guideline for Good Clinical Practice” as published in the Federal Register May 9, 1997, and all applicable Federal regulations including 21 CFR parts 50, 54, 56, and 312 are adhered to.

### **14.2. Institutional Review Board (IRB)/Independent Ethics Committee (IEC)/Research Ethics Board (REB) Approval**

This protocol and any accompanying material to be provided to the patient (such as advertisements, patient information sheets, or descriptions of the study used to obtain informed consent) will be submitted, by the investigator, to an IRB/IEC/REB. Approval from the IRB/IEC/REB must be obtained and a copy must be provided to Galera Therapeutics, Inc. or its representatives before initiating the conduct of any study procedures including screening or enrolling any subjects into the trial.

No modifications or deviations from this protocol other than those that are deemed medically necessary by the Principal Investigator or designated sub-investigator are to be made. Any protocol deviations will be reported to Galera Therapeutics, Inc. and to the IRB/IEC/REB in accordance with its reporting policy.

Any modifications made to the protocol by the sponsor after receipt of IRB/IEC/REB approval must be submitted to the committee for approval prior to implementation.

### **14.3. Written Informed Consent**

In accordance with regulatory and local IRB/IEC/REB requirements, before study procedures are performed, subjects will be informed about the study and required to sign the IRB/IEC/REB approved ICF. This form will be signed after adequate explanation of the aims, methods, objective and potential hazards of the study and prior to undertaking any study-related procedures. The Sponsor or its designee will provide an ICF template to the investigator. The Sponsor or its designee must approve changes to the ICF template prior to submission to the IRB/IEC/REB. Informed consent will be obtained according to the applicable IRB/IEC/REB requirements. No patient is to be screened or treated until an ICF, written in a language in which the patient or his/her legally authorized representative is fluent, has been obtained. The signed ICF will be retained with the study records. Each patient will also be given a copy of his/her signed ICF.

### **14.4. Data Monitoring Committee**

An independent Data Monitoring Committee (DMC) will be responsible for safeguarding the interests of the subjects by reviewing study data and providing recommendations about whether

the study is safe to proceed with ongoing enrollment as written and whether a protocol modification is required. The DMC will receive weekly updates on SAEs considered to be at least possibly related to study drug and will make a recommendation based on monthly cumulative summaries of these possibly related SAEs. The DMC will also be convened for review of available unblinded safety data and summaries of clinical data determined by the DMC to be relevant after 20 subjects have completed blinded dosing of GC4419/placebo, and may convene other meetings at its discretion. The DMC may recommend that further dosing of study treatment be discontinued and enrollment be halted pending further review if it finds that either a) more than 20% of GC4419 subjects require treatment discontinuation because of the protocol's criteria for dose reductions and discontinuation or b) the incidence of possibly related serious adverse events in the GC4419 arm constitute an unacceptable safety risk.

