An independent Data Monitoring Committee (DMC) will monitor ongoing safety results. The DMC will promptly receive all reports of Serious Adverse Events (SAEs). The DMC will also be convened for review of available safety data after 20 subjects have completed blinded dosing of GC4419/placebo, and may convene other meetings at its discretion. If upon review the DMC finds that more than 20% of experimental arm subjects require that GC4419 be discontinued according to the rules in this section, OR if the DMC finds an increase in serious or severe adverse events sufficient to constitute an unacceptable safety risk associated with GC4419, all dosing of GC4419/placebo for subjects on study will be discontinued, enrollment to the study will be terminated, and data reviewed with FDA prior to the sponsor considering additional dosing with GC4419 in this patient population.

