#### **10.6. Relationship to Study Drug**

All AEs will be categorized by the investigator with respect to their relationship to GC4419/placebo. The relationship between GC4419/placebo and the AE may be considered related, possibly related, or unrelated. The criteria for each category are listed below:

- **Related:** It is likely that GC4419/placebo caused or contributed to the cause of the AE or laboratory abnormality, when the temporal sequence from the time of GC4419/placebo administration, the known consequences of the patient's clinical/state condition or study procedures, the effects of discontinuing or re-introducing GC4419/placebo on the AE, and other medically relevant factors are considered.

- **Possibly Related:** There is a reasonable possibility that the AE or laboratory abnormality was caused by GC4419/placebo, when the temporal sequence from the time of GC4419/placebo administration, the known consequences of the patient's clinical state/condition or study procedures, and other medically relevant factors are considered.
- **Unrelated:** The investigator has a high level of certainty that the patient's clinical state/condition, study procedures, or other medically relevant factors other than treatment with GC4419/placebo caused the AE or laboratory abnormality. This relationship category should only be used when a clear precipitating cause exists, and it is not reasonably possible that the event is caused by treatment with GC4419/placebo.

If the relationship between the AE/SAE and the investigational product is determined to be "possibly related" the event will be considered to be related to the investigational product for the purposes of expedited regulatory reporting.

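### The Synopsis and Section 14.4 disagree on which SAEs the DMC receives and judges; read alone, 14.4 schedules no by-arm review of deaths judged unrelated after the 20-subject look

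*Combined protocol and SAP*

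**What the plan says.** The protocol describes the DMC's information in three places.

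- **Synopsis, Safety Monitoring and Toxicity Management.** "The DMC will promptly receive all reports of Serious Adverse Events (SAEs"), with no condition on causality. The safety criterion applies "if the DMC finds an increase in serious or severe adverse events sufficient to constitute an unacceptable safety risk associated with GC4419".
- **Section 14.4.** "The DMC will receive weekly updates on SAEs considered to be at least possibly related to study drug", and the committee "will make a recommendation based on monthly cumulative summaries of these possibly related SAEs". The section does not say that these summaries are split by arm. It adds one scheduled review: "The DMC will also be convened for review of available unblinded safety data and summaries of clinical data determined by the DMC to be relevant". The timing of that review, and the room for others, is given separately: "after 20 subjects have completed blinded dosing of GC4419/placebo, and may convene other meetings at its discretion". Criterion (b) refers to possibly related SAEs in the GC4419 arm.
- **Section 11.6.1.** The DMC "will perform an unblinded safety review while subjects in the study receive GC4419/Placebo (Section 14.4"). It sets no schedule of its own and points to 14.4.

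Three other sections bear on the point. Section 10.4.2 makes any fatal event an SAE. Section 10.6 says of the category *unrelated*: "This relationship category should only be used when a clear precipitating cause exists". The same sentence adds a second condition, that drug causation is not reasonably possible, and the definition also asks the investigator to be highly certain. Section 10.5.1 lets the investigator record natural disease progression as a non-serious AE and makes no exception for fatal events.

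**The concern.** Death is both the primary endpoint (Section 11.5.1) and the gravest possible harm, in a population where GC4419 had not been studied before (Section 5.1.1). The planning assumption is that half of control subjects die by Day 28. When an event is that common, a blinded investigator judging one death at a time has no means of seeing that one arm has too many. Only a comparison of counts by arm can show it.

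The drug's anticipated effect is hypotension (Section 9.1), and hypotension needing vasopressors is also a feature of critical COVID-19 (Section 4.1.1). Drug harm and disease course can therefore look alike at the bedside. If relatedness decides what the DMC sees between formal looks, the committee depends on the judgement least able to detect excess mortality. A DMC statistician or an IRB also cannot tell from the protocol which of the two descriptions governs.

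**Working it through.** **1. The plan's own figure.** Inputs from Section 11.2: 25 per arm, 28-day survival 50% against 90%, two-sided alpha 0.05, power about 80%. In terms of deaths the rates are 0.50 and 0.10, with mean 0.30. With a continuity correction of 1/25 = 0.04:

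- null SE = sqrt(2 × 0.30 × 0.70 / 25) = 0.1296
- alternative SE = sqrt((0.50 × 0.50 + 0.10 × 0.90) / 25) = 0.1166
- z = (0.40 − 0.04 − 1.96 × 0.1296) / 0.1166 = 0.909, so power = 81.8%

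Exact enumeration with Fisher's test gives 83.3%. The stated figure is reproduced. The point does not depend on it, but the same death rates are used below.

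**2. The texts side by side.**

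| Item | Synopsis | Section 14.4 |
|---|---|---|
| SAE feed | All SAE reports, promptly | Weekly, at least possibly related |
| Basis of monthly recommendation | Not stated | Possibly related SAEs |
| Scheduled review | After 20 complete dosing | Same, stated to be unblinded |
| Safety criterion | Increase in serious or severe AEs | Possibly related SAEs in the GC4419 arm |
| Consequence | Dosing and enrolment stop | DMC may recommend a halt |

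The feed, the criterion and the consequence all differ.

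**3. Subjects and deaths beyond the scheduled look.** Assume exactly 20 subjects, 10 per arm, inform it. Then 50 − 20 = 30 remain, 15 per arm. Expected deaths D among them are 15 × (control rate + GC4419 rate):

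- design alternative, 50% and 10%: 15 × 0.60 = 9, of 15 in the whole trial
- 50% in both arms: 15 × 1.00 = 15, of 25
- 60% in both arms (top of the 50–60% range in Section 4.1.1): 15 × 1.20 = 18, of 30

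In each case this is 60% of expected deaths. Thirty subjects is an upper figure, because the trigger is completion of dosing and enrolment may have passed 20 by then. In the other direction, dosing lasts 7 days and the endpoint runs to Day 28, so some deaths among the first 20 may also come after the look.

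**4. Share missing from the 14.4 feed.** Let f be the fraction of deaths called at least possibly related. Deaths absent from the feed = D × (1 − f). The documents give no value for f, so the whole range is shown:

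| f | D = 9 | D = 15 |
|---|---|---|
| 0 | 9 | 15 |
| 0.5 | 4.5 | 7.5 |
| 1 | 0 | 0 |

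The two conditions in Section 10.6 push doubtful cases into *possibly related*, so a value of f near zero cannot be presumed.

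**5. Whether copying the Synopsis would suffice.** An all-SAE feed carries only events reported as SAEs. Section 10.5.1 allows disease progression to be reported as non-serious without excepting death, so a death attributed to COVID-19 could miss even that feed. Deaths need to be named separately.

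**The case against.** The strongest reply is that the two passages can operate together: individual reports of every SAE under the Synopsis, plus a digest of related ones under 14.4. Section 14.4 does not say that its weekly updates are all the DMC receives, and nothing gives 14.4 precedence. The DMC also has a general remit to review study data, chooses the clinical summaries for the 20-subject review, and may meet whenever it wishes. Its charter is a separate document, which is where table shells and by-arm schedules could sit.

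Much of this stands. A reader might infer that excess mortality would run unseen to the end of enrolment. That would require the Synopsis to be disregarded, the DMC to request nothing and the charter to be silent, and the documents establish none of these. A reader might also infer that most deaths would be classed as unrelated because COVID-19 is always an available cause. That overlooks the second condition in Section 10.6 and the certainty it demands.

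It can also be said that the table would prove little. Suppose GC4419 mortality were 70% against 50% (an assumption with no basis in the documents). Expected deaths in 15 per arm are 15 × 0.70 = 10.5 and 15 × 0.50 = 7.5. A result of 11/15 against 8/15 gives Fisher p = 0.45, and two-sided Fisher power at 0.05 is about 10% with 15 per arm and 23% with 25. This limits what the table could prove. It does not argue for leaving deaths out, since a DMC weighs trends and case detail and is not bound to a significance test.

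The compatibility argument does not cover the monthly recommendation, which 14.4 ties expressly to possibly related SAEs, or the two safety criteria, which differ in scope.

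**Conclusion.** The protocol contradicts itself on what the DMC is sent and on the safety criterion it applies. Taken alone, Section 14.4 schedules no by-arm review of deaths judged unrelated after the single look at 20 completed subjects. That leaves up to about 30 of 50 subjects, with about 9 expected deaths under the design alternative and 15 at 50% mortality in both arms. These counts assume a look at exactly 20 subjects split evenly between arms.

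The documents do not support saying that the DMC will be kept from seeing these deaths, or how many the relatedness filter would remove. The finding is one of conflicting instructions and a missing scheduled comparison. It does not show that harm would go undetected. The statistical reason to act rests on no attribution rate: relatedness judged blind, one case at a time, cannot reveal a difference between arms in an outcome this frequent.

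**What to change.** Reconcile the Synopsis, Sections 11.6.1 and 14.4 and the DMC charter, using the same text throughout:

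- The DMC receives all SAEs and all deaths regardless of causality, including deaths recorded as natural progression under Section 10.5.1.
- Each monthly cumulative summary tabulates deaths and SAEs by arm. Relatedness is a column in that table and is not used as a filter.
- The two versions of the DMC safety criterion, and of what follows when it is met, are reconciled. Which version should govern is for the sponsor and the DMC to decide.

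The by-arm monthly table goes beyond what the Synopsis promises. It is recommended because an all-SAE feed alone would neither compare arms nor be sure to include every death. The cost is protocol and charter wording and one table from data already collected, with a slightly larger monthly DMC package.

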## **15. DATA HANDLING AND RECORDKEEPING**

### **15.1. Case Report Forms**

All required study data must be recorded on the electronic CRF provided by Galera Therapeutics, Inc. or its representatives. The data recorded onto the electronic CRF is derived from the source documents. The investigator shall ensure that all data in the electronic CRF is accurate and consistent with the source documents or that any discrepancies of the electronic CRF with source documents are explained (ICH E6 4.9.2).

Electronic CRFs will be accessed by the study center for collection of all study data, and a copy of the electronic CRF will be provided to the site for the investigator files. For each patient who is randomized to the study, the electronic CRF must be completed by site staff and must be signed electronically by the principal investigator in a timely fashion after data collection. If a patient withdraws from the study, the electronic CRFs should be promptly completed and the reason for withdrawal must be noted. If a patient is withdrawn from the study because of a drug-related toxicity, thorough efforts should be made to clearly document the outcome.

The sponsor will ensure that the electronic CRF selected meets the requirements per ICH E6 R2 with regard to data collection and handling, system maintenance, system security measures, change control, data backup, recovery, contingency planning, and decommissioning.

